Primary clinical endpoints will be the safety and preliminary efficacy of the study products, the latter defined as incidence of BV by Amsel criteria, BV by Nugent score (Nugent 7-10), intermediate microbiota (Nugent 4-6), TV by culture and symptomatic vaginal candidiasis (by wet mount) during follow-up. Secondary clinical endpoints will be membership of specific VMB clusters over time as determined by clustering analysis of all available Illumina MiSeq data, the presence over time of individual VMB bacteria (as determined by Illumina MiSeq), and the incidence of STIs (HIV, syphilis, HSV-2, CT, and NG), and UTI (by urinalysis dipstick) during the follow-up period. In addition, we will conduct focus group discussions (FGDs), in-depth interviews (IDIs) and a quantitative survey to address specific feasibility objectives (see 4.2 below).

Primary clinical objectives	Endpoints
1. To determine the safety of the three biomedical interventions compared to the control group.	 Self-reported solicited and unsolicited (serious) adverse events (AEs) and social harms Clinician-observed speculum exam findings
2. To determine the preliminary efficacy of the three biomedical interventions compared to the control group in reducing BV recurrence.	 BV by Amsel criteria, Nugent score 4-10, TV by culture and symptomatic vaginal candidiasis at any time during the intervention (Day 7, Month 1, Month 2) BV by Amsel criteria, Nugent score 4-10, TV by culture, and symptomatic vaginal candidiasis after cessation of the intervention (Month 6) Abnormal Nugent scores will be analysed as two categories (4-6 and 7-10) instead of one category (4-10) if statistical power permits.
Secondary clinical objectives	Endpoints
1. To determine which VMB changes at the molecular bacterial level are induced by initiation and cessation of the various interventions compared to the control intervention.	 Membership of specific VMB clusters (as determined by clustering analysis of all Illumina MiSeq data) over time The presence over time of individual VMB bacteria as determined by Illumina MiSeq (and, if funding permits, other molecular methods), including the PPMs streptococci, staphylococci, and E coli. The additional data points in the frequent self-sampling group will be analysed separately.
2. To determine preliminary	 Incidence of the following STIs between screening and

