6.2 Intent-to-treat incidence rate ratios comparing product use groups to the control group

IRRs with 95% confidence intervals will be calculated comparing each product use group (groups 2-4) to the control group (group 1) using the IR function in STATA. In addition, IRRs with 95% confidence intervals will be calculated comparing each vaginal probiotic group (group 3 and 4) to the metronidazole group (group 2). As before, these IRRs will be calculated for each primary efficacy outcome and for each of the three time periods: between the Enrolment visit and the M2 visit (during product use), between the M2 visit and M6 visit (after cessation of product use) and for the entire study period after randomisation. They will be reported in the following table (one table for each time period):

	Group 2 vs 1 IRR (95% CI)	Group 3 vs 1 IRR (95% CI)	Group 4 vs 1 IRR (95% CI)	Group 3 vs 2 IRR (95% CI)	Group 4 vs 2 IRR (95% CI)
Incident BV by					
modified Amsel					
criteria					
Incident Nugent 4-10					
Incident Nugent 7-10					
Incident TV by culture					
Incident symptomatic					
vaginal candidiasis					

6.3 Per protocol incidence rate ratios comparing product use groups to the control group

A few significant protocol deviations occurred that could have an impact on the primary analysis results:

- CT/NG PCR testing was not available at the RU clinic and was outsourced to the National Reference Laboratory in Kigali, Rwanda. Test results were usually available only weeks after sample collection. We realised that this might be an issue early on and increased the sample size of each randomisation group to 17 instead of 15 to allow for exclusion of women who were randomised while having an ongoing CT or NG infection. Unfortunately, the number of women with a CT or NG infection in each randomisation group turned out to be higher than expected: 8/17 in Group 1, 7/17 in Group 2, 4/17 in Group 3, and 7/17 in Group 4 (Fisher's exact p = 0.53).
- Discrepancy between modified Amsel criteria and Nugent score at the Enrolment visit: Women could be enrolled if they had negative modified Amsel criteria after having completed the 7-day metronidazole treatment. Nugent scores became available later. In a handful of cases, women who were randomised because they no longer had BV by modified Amsel criteria turned out the have a Nugent score of 7-10 at the Enrolment visit.

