7.3 Adverse events: structurally assessed at each study visit

Some safety outcomes were structurally assessed at each study visit as part of the face-to-face interview and pelvic and bimanual examination. Laboratory test results will not be included because they are covered under the primary and secondary efficacy outcomes. The safety outcomes will be reported as the number of women who experienced the event at least once during the time period by study group. Differences between the randomisation groups will be assessed by Fisher's exact test. If the p-value is < 0.05, pairwise comparisons (also using Fisher's exact test) between study groups will be conducted. If an AE occurred more than once in individual women, the analysis will be repeated for the number of events (as opposed to number of women) per study group. All analyses will be done for three time periods: between the Enrolment and M2 visits (during product use), between the M2 and M6 visits (after cessation of product use), and for the overall follow-up period between the Enrolment and M6 visits.

Number of women	Group 1	Group 2	Group 3	Group 4	p-
Between Enrolment – M2	N=17	N=17	N=17	N=17	value ¹
Any patient-reported urogenital symptoms (n %)					
If yes, symptoms reported (n % for each) ² :					
– Burning when passing urine					
 Frequent urination or urgent need to urinate 					
– Blood in urine					
– Genital burning					
– Genital itching					
– Pain during sex					
– Lower abdominal pain					
– Unusual vaginal discharge					
– Sores in the genital and/or anal area					
(including buttocks)					
– Other (describe in footnote)					
Any abnormal findings during pelvic exam					
clinician-observed (n %)					
If yes, findings observed (n % for each) ² :					
– Abnormal (genital) odour					
 Enlarged/tender inguinal lymph node 					
 Condylomata (any location genitalia) 					
 Ulcers/blisters suggestive of STI on vulva 					
 Any other lesion on vulvar epithelium 					
 Abnormal vaginal discharge 					
–Vaginal mass (polyp, myoma, etc.)					
 Ulcers/blisters suggestive of STI in vagin 					
 Any other lesion on vaginal epithelium 					
 Abnormal cervical discharge/pus 					
 Any lesion on cervical epithelium 					
 Other (describe in footnote) 					
Any abnormal findings during bimanual exam					
clinician-observed (n %)					
If yes, findings observed (n % for each) ² :					
– Uterine mass					
– Adnexal mass					
- Uterine tenderness					
– Adnexal tenderness					

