7.4 Adverse events: not structurally assessed

In addition to the safety outcomes that were structurally assessed, the study physician also asked the following questions at each study visit: Since your last study visit, did you experience any other new physical complaints or were you diagnosed with any other new conditions? Since your last study visit, have you taken any new medications? The answers given to those questions, and any other spontaneously reported adverse events, will be coded using MedDRA (version 19.0, March 2016) and will be reported in the same manner as described above for the structurally assessed adverse events.

8. Analyses of follow-up data: secondary efficacy outcomes

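### SAP 7.3 and 7.4 plan no product-versus-control estimate or confidence interval for adverse events, and run pairwise tests only after a significant four-group Fisher test

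*SAP*

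**What the plan says.** The Protocol's table of objectives (sections 4.1 to 4.2), repeated in SAP section 2, sets primary objective 1: "To determine the safety of the three biomedical interventions compared to the control group".

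SAP 7.3 covers symptoms, pelvic and bimanual findings, and clinical diagnoses:

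- Summary: "The safety outcomes will be reported as the number of women who experienced the event at least once during the time period by study group".
- First test: "Differences between the randomisation groups will be assessed by Fisher's exact test". The table shell has four group columns headed N=17 and a single p-value column.
- Second step: "If the p-value is < 0.05, pairwise comparisons" follow, again by Fisher's test. This covers all six pairs, without priority for control.
- Repetition: "All analyses will be done for three time periods". Where an event recurs within a woman, the analysis is repeated on numbers of events.

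SAP 7.4 says that all other adverse events "will be reported in the same manner as described above for the structurally assessed adverse events".

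Neither section names a risk difference, a ratio or a confidence interval. In contrast, SAP 6.2 plans incidence rate ratios with 95% intervals for each product against control for every primary efficacy outcome, with no preliminary test. SAP 8.1 does the same for secondary outcomes for which it concedes that the study is too small.

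**The concern.** The objective asks how each product compares with control. The planned safety tables show the counts side by side but do not estimate that comparison or say how precisely it is known. A formal product-versus-control result appears only if a test of a different hypothesis (any difference among four groups) is significant.

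The Protocol describes the study as a descriptive pilot whose data will help choose interventions for an efficacy trial. For that purpose the useful safety result is the size of excess risk that the data still allow for each product. At 17 women per group this can be large even when the p-value is unremarkable. The primary safety objective therefore gets weaker reporting than the secondary infection outcomes in the same SAP.

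**Working it through.** **Inputs.** Group size is 17: SAP 6.3 says the investigators "increased the sample size of each randomisation group to 17 instead of 15", and the 7.3 shell uses N=17. The threshold is 0.05, taken as two-sided because sidedness is not stated. Adverse event rates are not given in either document, so those below are assumptions. All 17 women per group are taken as evaluable.

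**Plan's own figure.** No power, margin or sample size is stated for safety, so there is none to reproduce. The one four-group Fisher p printed at this size is the CT/NG comparison in SAP 6.3 (8, 7, 4, 7 of 17; p = 0.53). Exact calculation gives 0.54. The small gap does not matter here.

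**Method.** All 18^4 possible outcomes were enumerated. Each was given its exact four-group (Freeman-Halton) p and its 2x2 Fisher p for product versus control, and weighted by its binomial probability.

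**How often the condition is met, and what it hides.** The last column is the probability that one given worse product is significant against control while the four-group p is 0.05 or more. Differences were taken before rounding.

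| True risk: control; products | Four-group p<0.05 | Product v control p<0.05, no condition | Same, with condition | Hidden |
|---|---|---|---|---|
| 10%; one at 30%, others 10% | 28.8% | 18.6% | 15.3% | 3.3% |
| 10%; all three at 30% | 24.9% | 18.6% | 13.9% | 4.7% |
| 5%; one at 25%, others 5% | 37.2% | 22.0% | 19.3% | 2.8% |
| 10%; one at 40%, others 10% | 55.6% | 39.2% | 35.9% | 3.3% |
| 10%; one at 50%, others 10% | 79.5% | 62.6% | 60.6% | 2.0% |

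With all three products at 30% against 10%, the chance that at least one of the three control contrasts is significant but hidden is 12.7%.

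**Worked example: 1, 4, 4, 7 of 17.** The four-group p is 0.127, so SAP 7.3 stops. For Group 4 versus control:

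- Difference: 7/17 − 1/17 = 41.2% − 5.9% = 35.3 points.
- Wilson limits: 21.6% to 64.0% for 7/17; 1.0% to 27.0% for 1/17.
- Newcombe lower limit: 0.353 − √[(0.412 − 0.216)² + (0.270 − 0.059)²] = 0.065.
- Newcombe upper limit: 0.353 + √[(0.640 − 0.412)² + (0.059 − 0.010)²] = 0.586.
- Fisher p: 2 × [C(17,1)·C(17,7) + C(17,8)] / C(34,8) = 2 × (330,616 + 24,310) / 18,156,204 = 0.039.

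**Opposite discordance: 1, 1, 1, 6 of 17.** The four-group p is 0.027, but 6/17 against 1/17 gives p = 0.085. Pairwise testing is triggered and finds no significant pair.

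**What intervals would show in quiet rows.**

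- 5/17 v 2/17: +17.6 points (−10.1 to +42.8). With the other groups at 2/17, the SAP would give only the counts and p = 0.51.
- 2/17 v 2/17: 0 (−24.1 to +24.1).
- 0/17 v 0/17: 0 (−18.4 to +18.4).

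**The case against.** The best defence is that the first-step test is not what limits the information. At 10% v 30%, an unconditional product-versus-control test is significant in only 18.6% of trials. At 5% v 25% in one product, the four-group test is significant more often than the pairwise test (37% against 22%). These figures mostly reflect 17 women per group, which no rewording changes. This stands.

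Counts and percentages per group are printed for about 35 rows in each of three periods, so a reader can compute any difference and interval. An overall test before pairwise tests is also a conventional restraint over roughly 35 × 3 = 105 tests. Both points are true. They lower the severity, but a pre-specified analysis should itself deliver the comparison that its objective names. The restraint also works only within a row.

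Three stronger readings are tempting, and the documents do not support them:

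- **The safety objective rests on a single p-value.** There is one p-value per row and period, always beside the group counts.
- **No harm outcome has an interval.** Symptomatic candidiasis and UTI have rate ratios with 95% intervals in SAP 6.2 and 8.1, as do the other laboratory infections. The text of SAP 7.1 and 7.2 (serious adverse events, social harms) was not available for this review, so nothing can be said about it.
- **The plan treats non-significance as safety.** Neither document says so. It is a risk of misreading.

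**Conclusion.** The point holds for SAP 7.3 and 7.4 only. They plan no product-versus-control estimate or interval, although that comparison is primary objective 1 and the efficacy sections provide one. The missing interval is the main loss: 5/17 against 2/17 is compatible with an excess of up to 43 points, and the planned output would not say so.

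The p<0.05 condition is secondary. It is met in about 25 to 37% of trials in the 10% v 30% and 5% v 25% cases, and in about 80% at 10% v 50% in one product. It hides a given nominally significant control contrast in about 2 to 5% of trials, or any of three in 12.7% when all products are at 30% against 10%. It would be wrong to infer that the condition usually suppresses a clear harm: for a large excess it usually opens.

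All of these probabilities rest on assumed event rates, 17 evaluable women per group and two-sided tests. Severity: should-fix, because the counts are reported and the comparison can be recovered from them.

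**What to change.** In SAP 7.3, and so in 7.4:

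1. Remove the p<0.05 condition for the comparisons of Groups 2, 3 and 4 with Group 1.
2. Report each risk difference with a 95% Newcombe or exact interval. Do this at least for the summary rows (any symptom, any pelvic finding, any bimanual finding, and the diagnoses) and for every row with at least one event.
3. For the repeat analysis by number of events, use a rate ratio or rate difference with a 95% interval, because a risk difference does not apply to recurrent events. State how repeat events in one woman are handled.
4. Keep the four-group Fisher p as a supplementary column, and state that a non-significant p is not evidence of safety.

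The cost is SAP wording and three more table columns per period, with no new data. The intervals will be wide and not adjusted for multiplicity, and the SAP should say so. Limiting them to summary rows and rows with events avoids long runs of 0/17 against 0/17.

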6.8 Unscheduled visits

All participants will be encouraged to visit the RU clinic in between study visits when they experience SAEs, AEs that they suspect are product-related, or new episodes of STIs, BV or vaginal candidiasis. Study staff may ask participants to return to the RU clinic in between regular study visits if diagnostic tests come back positive and require counselling, partner notification, treatment and/or referral. Other unscheduled visits may take place at the request of participants or study staff at any time during the study. All unscheduled visits will be documented.

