3.4 Numbers of and reasons for unscheduled visits

Time period	Number of women	Number of visits
Between the Screening and Enrolment visits (not including		
Results visits scheduled by RU staff)		
Between Enrolment and M1		
Between M1 and M2		
Between M2 and M6		
After M6		
TOTAL		

Reasons for unscheduled visits	Number of visits
To withdraw informed consent	
To obtain additional study product supplies	
To report an (S)AE or social harm	
To test for an STI or vaginal infection	
To test for a UTI	
To collect treatment for a positive lab result	
Wants to be tested for HIV or pregnancy	
For male partner HIV/STI testing and couple counselling	
To ask questions or express concerns	
Other (each reason will be listed)	
TOTAL	

4. Analyses of baseline data

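### SAP 7.3 repeats its Fisher's exact comparison on numbers of adverse events when an event recurs within women, with no event denominator and no allowance for within-woman correlation

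*SAP*

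**What the plan says.** SAP 7.3 covers symptoms, pelvic findings and bimanual findings assessed at every visit. The main measure is "reported as the number of women who experienced the event at least once" in the period, by group. One test is named: "Differences between the randomisation groups will be assessed by Fisher's exact test". "If the p-value is < 0.05, pairwise comparisons" follow, again by Fisher's exact test. Where an AE happened more than once in individual women, "the analysis will be repeated for the number of events (as opposed to number of women) per study group". The periods are Enrolment to M2, M2 to M6, and Enrolment to M6, and the table template shows N=17 per group.

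SAP 7.4 extends this to AEs not structurally assessed, including "any other spontaneously reported adverse events": they "will be reported in the same manner as described above for the structurally assessed adverse events".

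Neither section says what the event counts are divided by, how several events from one woman are handled, or when a finding seen at two successive visits counts as a second event. The SAP does use GEE for repeated outcomes, but only for the Nugent outcomes in 6.4.

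**The concern.** No test other than Fisher's appears in 7.3, so repeating the analysis means running the four-group Fisher test, and its pairwise follow-up, on event totals. That test treats every unit as a separate independent observation. The woman is the unit that was randomised, and she can supply up to three scheduled reports on product and four overall. A woman with genital itching at one visit is more likely than her neighbours to report it at the next.

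Safety is primary objective 1. A complaint that keeps returning in two or three women could give a small event-level p-value, open the pairwise comparisons and produce a product-versus-control result below 0.05, while the count of women shows nothing of the kind.

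**Working it through.** The SAP prints no AE rate or p-value for this analysis, so there is no figure of its own to reproduce.

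**Inputs from the documents.** 17 women in each of four groups (SAP 4.2, 6.3 and 7.3). Three scheduled visits from Enrolment to M2 (D7, M1, M2) and four to M6 (SAP 1.1). Threshold 0.05 (SAP 7.3).

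**Assumptions.** Woman-visits as the event denominator: 17 × 3 = 51 or 17 × 4 = 68 per group. Full attendance. Risk per visit 10%. Within-woman correlation 0 to 0.5. The documents give none of these.

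**1. The denominator.** If the template's N=17 is kept, three visits allow up to 51 events in a group and four allow up to 68. The count can exceed N, and the two-row table that Fisher's test needs no longer exists. Woman-visits avoid this for scheduled visits. They do not fit unsolicited reports, which are not limited to one per visit.

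**2. Error rate with no true difference.** With V visits and correlation ρ, the variance of an event total is multiplied by D = 1 + (V − 1)ρ. For a four-group comparison (3 degrees of freedom, 5% critical value 7.815), the rejection rate is roughly P(χ²₃ > 7.815/D).

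| ρ | D, V=3 | Rejection, V=3 | D, V=4 | Rejection, V=4 |
|---|---|---|---|---|
| 0 | 1.0 | 5% | 1.0 | 5% |
| 0.1 | 1.2 | 9% | 1.3 | 11% |
| 0.3 | 1.6 | 18% | 1.9 | 25% |
| 0.5 | 2.0 | 27% | 2.5 | 37% |

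Simulating the exact test itself (beta-binomial events, 10% visit risk) agrees: about 5% at correlation 0, 8% to 11% at 0.1, 16% to 25% at 0.3 and 27% to 40% at 0.5. In the same data the test on numbers of women rejects in 4% to 5%.

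**3. Example, Enrolment to M2.** Three women in Group 2 have 3, 3 and 2 events; one woman in each other group has 1. The p-value sums the probabilities of all tables with the same margins that are no more likely than the observed one.
- By women, 1, 3, 1, 1 of 17: p = 0.71. The pairwise step is not reached.
- By events, 1, 8, 1, 1 of 51: p = 0.005. Group 2 vs 1, 8/51 vs 1/51: p = 0.03.
- Permuting whole women between groups: p = 0.08 or 0.13, depending on the statistic.

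**4. How extreme the example is.** Three women over three visits can have at most 9 events. Keep the same women and vary Group 2's total:

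| Group 2 events | Four-group p | Group 2 vs 1 p |
|---|---|---|
| 4 | 0.37 | 0.36 |
| 5 | 0.20 | 0.20 |
| 6 | 0.039 | 0.11 |
| 7 | 0.014 | 0.06 |
| 8 | 0.005 | 0.03 |
| 9 | 0.002 | 0.016 |

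With one event in each other group, the pairwise result needs at least 8 of 9. With none elsewhere, 6 of 9 is enough: 0, 6, 0, 0 of 51 gives four-group p = 0.0008 and Group 2 vs 1 p = 0.027, while 0, 3, 0, 0 of 17 women gives p = 0.054.

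**5. Periods affected.** Mainly Enrolment to M2 and Enrolment to M6. M2 to M6 has one scheduled visit, but recurrence is possible there too. Protocol 6.8 states: "Other unscheduled visits may take place at the request of participants or study staff at any time during the study". SAP 3.4 lists "To report an (S)AE or social harm" among the reasons for such visits.

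**The case against.** **Recurrence is not dependence.** This stands. With independent visits at these risks, at least one woman would still have a repeat event in most trials, and the event-level test would hold its level. A reader might infer that the repeat is invalid whenever it is triggered. The documents do not support that: the fault needs positive within-woman correlation, which is likely for symptoms and lesions but which the documents do not quantify.

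**The example is near its ceiling.** This stands for that configuration, and step 4 shows the limit. It does not remove the problem, because 6 of 9 events with none in the control group is enough.

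**The consequence is small.** This stands in large part. The count of women is always reported beside the repeat, Protocol 4.3 calls the pilot descriptive, and no stopping, dosing or arm-selection rule refers to these p-values. A reader might infer that the primary safety analysis as a whole fails, or that a product would be wrongly dropped. The documents support neither.

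**Event rates would count a persisting finding repeatedly.** This stands. The list in 7.3 includes a uterine mass and condylomata, which may be seen at several visits. A rate needs a rule for what counts as a new event.

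**Conclusion.** The rule for repeat events gives unreliable p-values as written. It applies a test for independent units to events clustered within women, and it leaves the denominator open. The direction is certain for any positive correlation. The size is not: on the stated assumptions it runs from little inflation at correlation 0.1 (8% to 11%) to 27% to 40% at 0.5.

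Counting women is an appropriate unit of analysis and holds its level for a single test. That does not endorse everything in 7.3, which tests about 35 rows over three periods without adjustment; that is a separate matter. The correction is worth making because it concerns a primary objective and costs almost nothing, but the harm is limited to supplementary p-values in a pilot.

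**What to change.** Amend SAP 7.3, which carries over to 7.4:
- Restrict Fisher's exact test, four-group and pairwise, to numbers of women.
- Report repeat events per group as counts and rates per person-day. Count a finding that persists from one visit to the next once, as SAP 6.1 already separates incident from persistent infections.
- Leave these event figures untested, or test them with the woman as the unit, for example by permuting whole women with all their events between groups. In null simulations at correlations 0.2 to 0.6, that test rejected in 3.9% to 5.4%.

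The cost is a sentence or two of SAP wording and no new data, since total person-days are already planned in SAP 3.1. The four-group test and its 0.05 gate stay as they are for women. The downside is that repeat events carry no p-value unless the permutation test is run, and someone must decide for each recurring finding whether it is new or persisting.
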